Effect of Short-Term Prednisone Therapy on C-reactive protein Change in Emergency Department Patients With Acute Heart Failure and Elevated Inflammatory Markers (CORTAHF)

Protocol Number: CHF202301

Principal Investigator:

[name], PhD
Emergency Department, Hôpital Universitaire Pitié-Salpêtrière,
Assistance Publique-Hôpitaux de Paris (AP-HP),
Paris, France

Medical Monitor:

[name]
Momentum Research, Inc.
[contact]
[contact]

Sponsor:

Heart Initiative
[name]

Funded by: Heart Initiative

Version Number: Final v. 2.0

5 January 2024

Protocol Signature Page

Protocol Title: Effect of Short-Term Prednisone Therapy on C-reactive protein Change in Emergency Department Patients With Acute Heart Failure and Elevated Inflammatory Markers (CORTAHF)

Protocol Version / Date: Final Version 2.0 dated 5 January 2024

Sponsor: Heart Initiative

Declaration of Investigator:

I confirm that I have read the above-mentioned protocol and its attachments. I agree to conduct the described trial in compliance with all stipulations of the protocol, regulations and ICH E6 Guideline for Good Clinical Practice (GCP).

Site Principal Investigator Name: _____

Site Principal Investigator Signature: _____

Date of Signature: _____

Summary of Changes from Previous Version:

Affected Section(s)	Summary of Revisions Made	Rationale
Throughout	Reference changed from study days 30 and 90 to study days 31 and 91.	To clarify that these assessments are to be performed 30 and 90 days after randomization, which are days 31 and 91 counting the day of randomization as day 1.
1.2	Timing between assessments corrected in study schema.	Previous intervals were incorrect, although corrected schema provided to investigators during pre-study training.
1 3 8.1.5 9.4.3 9.4.9	Secondary objective and endpoint revised to include all adverse events of worsening heart failure through day 91. The previous secondary endpoint, with a more restricted WHF definition, and more limited timeframe moved to tertiary/exploratory endpoint.	This is a small pilot study with a small number of events expected. A longer timeframe and less stringent definition of WHF should provide more power to detect an effect on this measure of mortality/morbidity.
3 9.4.9	Exploratory endpoints of length of stay in ICU and length of initial hospital stay limited to the 30 days following randomization	The vast majority of patients will be discharged before study day 31. However, in order to account for a few possible extreme values, these endpoints will be truncated at 30 days.
3 9.4.9	Dyspnea removed from list of HF symptoms.	Dyspnea on exertion will be captured using NYHA class. No separate measure of dyspnea will be captured.
1.3 8.1.7	Local laboratory assessments at days 2 and 4 are to be recorded if done but are not required.	To reduce site burden and study cost, these assessments will be optional and will be collected per local practice. The omission will not affect the main study objectives.
9.3	The main analysis will be performed in the per-protocol rather than the intention-to-treat analysis population. The ITT population will exclude patients randomized in error.	Because this is a small pilot study, a few inappropriately enrolled or treated patients can have a major effect on the findings. Thus, the main analysis will be conducted in the per-protocol population which excludes patients enrolled who were ineligible or who were not treated according to the allocated treatment. Analyses will exclude patients who were randomized in error, e.g., non-existent patients or patients found to be ineligible before study treatment started.
10.3	Amendment history updated to include this amendment.	Rationales for changes provided above.

Contents

STATEMENT OF COMPLIANCE	vi
1 PROTOCOL SUMMARY	1
1.1 Synopsis	1
1.2 Schema	4
1.3 Schedule of Activities (SoA).....	5
2 INTRODUCTION	6
2.1 Study Rationale	6
2.2 Background	6
2.3 Risk/Benefit Assessment.....	6
2.3.1 Known Potential Risks	6
2.3.2 Known Potential Benefits	7
3 OBJECTIVES AND ENDPOINTS	7
4 STUDY DESIGN	9
4.1 Overall Design.....	9
4.2 Scientific Rationale for Study Design	9
4.3 Justification for Dose.....	9
4.4 End of Study Definition	9
5 STUDY POPULATION	10
5.1 Inclusion Criteria.....	10
5.2 Exclusion Criteria.....	10
5.3 Lifestyle Considerations.....	11
5.4 Screen Failures	11
5.5 Strategies for Recruitment and Retention.....	11
6 STUDY INTERVENTION	12
6.1 Study Intervention(s) Administration.....	12
6.1.1 Study Intervention Description	12
6.1.2 Dosing and Administration.....	12
6.2 Preparation/Handling/Storage/Accountability.....	12
6.2.1 Acquisition and accountability	12
6.2.2 Formulation, Appearance, Packaging, and Labeling	12
6.2.3 Product Storage and Stability	12

11	REFERENCES.....	29
12	APPENDIX.....	31
12.1	EQ-5D Sample UK English Version.....	31

STATEMENT OF COMPLIANCE

The trial will be carried out in accordance with International Conference on Harmonisation Good Clinical Practice (ICH GCP) and any applicable local regulatory requirements. Investigators and clinical trial site staff who are responsible for the conduct, management, or oversight of this clinical trial have completed ICH GCP Training.

The protocol, informed consent form(s), recruitment materials, and all participant materials will be submitted to the Ethics Committee (EC) for review and approval. Approval of both the protocol and the consent form must be obtained before any participant is enrolled. The Principal Investigator will assure that no deviation from, or changes to the protocol will take place without prior agreement from the Sponsor, funding agency and documented approval from the EC, except where necessary to eliminate an immediate hazard(s) to the trial participants. In addition, all changes to the consent form will be EC approved; a determination will be made regarding whether a new consent needs to be obtained from participants who provided consent, using a previously approved consent form.

1 PROTOCOL SUMMARY

1.1 SYNOPSIS

- Title:** Effect of Short-Term Prednisone Therapy on C-reactive protein Change in Emergency Department Patients With Acute Heart Failure and Elevated Inflammatory Markers (CORTAHF)
- Study Description:** This is a multicenter, parallel-group, randomized, open-label, controlled trial. Patients with a diagnosis of acute heart failure (AHF) in the emergency department (ED) or after emergency presentation to hospital will be screened and informed of the study. After signed consent, patients will be randomized into the control group (usual AHF treatment) or intervention group (usual AHF treatment + prednisone). Prednisone will be given for 7 days. Patients will be assessed at days 2, 4 or at discharge if earlier, and at day 7 at hospital visit. If the patient has been discharged before day 7, a follow-up visit will be scheduled at day 7 for endpoints assessment followed by a scheduled hospital visit at day 31 and a telephone follow-up at day 91. Study drug will be dispensed for the patient to take home until day 7.
- Objectives:** Primary objective: to assess the effects of prednisone therapy started in the ED/hospital and continued for up to 7 days on the change of CRP level.
- Secondary objectives: to compare the effects of prednisone therapy on the occurrence of death, hospital readmission for HF, or worsening HF (WHF) through day 91; and on change in quality of life (QoL) as measured by the EQ-5D-5L questionnaire at day 7.
- Other objectives include comparisons on the effects on WHF, death or HF readmission through day 31, change in QoL at day 31, symptoms and signs of heart failure at day 7 including weight, and all-cause mortality or hospital readmission for HF through day 91.
- Endpoints:** Primary endpoint: change of CRP level, defined by CRP level at day 7 minus CRP level at inclusion
- Secondary Endpoints:
1. Time to first event of WHF adverse event, death, or hospital readmission for decompensated HF to day 91.
 2. Changes in quality of life measured by the EQ-5D-5L from randomization to day 7.
- Study Population:** 120 adult patients visiting the ED or presenting emergently to the hospital with a diagnosis of AHF and elevated markers of congestion and inflammation.
- Inclusion criteria:
1. Age 18 to 85 years of age
 2. Unplanned ED visit or hospital presentation within the 12 hours prior to Screening with acute or worsening dyspnea and/or orthopnea, and pulmonary congestion on chest X-ray or lung ultrasound.
 3. All measures from presentation to randomization of systolic blood pressure ≥ 100 mmHg, and of heart rate ≥ 60 bpm.

4. Written informed consent to participate in the study.
5. Biomarker levels indicative of congestion and inflammation: At Screening, NT-proBNP > 1,500 pg/mL and CRP > 20 mg/L
6. Patient agrees for follow-up visits at the hospital at day 7 in case of earlier discharge and Day 31.

Exclusion criteria:

1. Anticipated life expectancy less than 6 months
2. Mechanical ventilation (not including CPAP/BIPAP) prior to Screening.
3. Significant pulmonary disease contributing substantially to the patients' dyspnea such as FEV1 < 1 liter or need for chronic systemic or non-systemic steroid therapy, or any kind of primary right heart failure such as primary pulmonary hypertension or recurrent pulmonary embolism.
4. Myocardial infarction, unstable angina or cardiac surgery within 3 months, or cardiac resynchronization therapy (CRT) device implantation within 3 months, or percutaneous transluminal coronary intervention (PTCI), within 1 month prior to inclusion.
5. Index Event (admission for AHF) triggered primarily by a correctable etiology such as significant arrhythmia (e.g., sustained ventricular tachycardia, or atrial fibrillation/flutter with sustained ventricular response >130 beats per minute, or bradycardia with sustained ventricular arrhythmia <45 beats per minute), infection, severe anemia, acute coronary syndrome, pulmonary embolism, exacerbation of COPD, planned admission for device implantation or severe non-adherence leading to very significant fluid accumulation prior to admission and brisk diuresis after admission. Troponin elevations without other evidence of an acute coronary syndrome are not an exclusion.
6. Uncorrected thyroid disease, active myocarditis, or known amyloid or hypertrophic obstructive cardiomyopathy.
7. History of heart transplant or on a transplant list, or using or planned to be implanted with a ventricular assist device.
8. Sustained ventricular arrhythmia with syncopal episodes within the 3 months prior to screening that is untreated.
9. Presence at screening of any hemodynamically significant valvular stenosis or regurgitation, except mitral or tricuspid regurgitation secondary to left ventricular dilatation, or the presence of any hemodynamically significant obstructive lesion of the left ventricular outflow tract.
10. Primary liver disease considered to be life threatening
11. Renal disease or eGFR < 30 or > 80 mL/min/1.73m² (as estimated by the simplified MDRD formula) at inclusion or history of dialysis.
12. Systemic steroid therapy, within 30 days from inclusion.
13. Inability to consent, or patient under guardianship measure
14. Participation in another intervention trial in the past 30 days
15. Anticipated non-adherence to study protocol or follow-up.
16. Pregnant or nursing (lactating) women.
17. Known hypersensitivity to steroids or constituents of prednisone tablets (excipients)

18. Psychotic states not yet controlled by treatment
19. Concomitant administration of live vaccines and up to 3 months after end of corticotherapy administration.
20. Patient under legal protection measure (tutorship or curatorship) and patient deprived of freedom
21. Persons subject to psychiatric care without their consent

Phase:

N/A

Description of Sites/Facilities

5 hospitals in Armenia

Enrolling Participants:

Description of Study

Investigational product: Prednisone 40 mg once a day, for up to 7 days added to usual care medications.

Intervention:

Comparator: Usual care alone.

[figure not shown]
Study Duration:

13 months (including recruitment (12 months), Follow up (1 month for the last patient enrolled)

Participant Duration:

91 days

1.2 SCHEMA

1.3 SCHEDULE OF ACTIVITIES (SOA)

Assessment	Visit 1	Visit 2	Visit 3	Visit 4	Visit 5	Visit 6 Telephone Contact
	Inclusion and randomization, ≤ 12h after ED/hospital presentation	Day 2 ~24 hours after randomization	Day 4 ~72 hours after randomization, or discharge if earlier	Day 7 7 (+/-1) days after randomization	Day 31 30 (+/- 5) days after randomization	Day 91 90 (+/- 5) days after randomization
Eligibility	X					
Pregnancy test for women of childbearing age	X					
Medical history	X					
Chest X-ray/ lung US*	X					
ECG*	X					
Echocardiography†	X					
Concomitant medications	X	X	X	X	X	
NT-proBNP, Tn, CRP	X	X (CRP only)	X (CRP only)	X (CRP only)	X	
Local labs: Hgb, serum sodium, glucose, potassium and kidney function measures, WBC count, % lymphocytes, liver function	X	X§	X§	X	X	
Physical exam including vital signs and clinical HF assessment	X	X	X	X	X	
EQ-5D-5L	X			X	X	
Biobanking samples	X		X	X	X	
Randomization	X					
Study drug prednisone‡ or usual care	X (seven days of treatment for investigational arm only)					
Clinical outcomes	←-----X----->					X
Adverse events	<-----X----->					

*Non-study assessment considered standard of care required for study eligibility.

†Non-study assessment considered standard of care which should have been performed within 6 months prior to inclusion, including during the current admission.

‡In patients randomly assigned to active intervention.

§To be recorded if done per local practice, but not required.

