8.1.6 Other clinical outcomes

Deaths will be recorded through 90 days post-randomization. The primary cause will be recorded when possible. Every effort (consistent with all applicable laws and regulations) will be made to obtain vital status on all randomized subjects.

The length of stay in an intensive care unit (ICU) or other acute care unit and the total length of hospital stay will be recorded for the initial hospitalization and of each rehospitalization through 90 days following randomization. The primary reason for the readmission to the hospital will be recorded. A rehospitalization is defined as an unplanned overnight stay in the hospital, regardless of whether the patient was admitted.

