9.4.3 Analysis of the Secondary Endpoint(s)

Treatment groups will be compared with respect to the occurrence of a WHF adverse event, or HF readmission, or death from any cause from randomization through day 91 with a log-rank test stratified by study center. The time to event will be calculated as the date of the first occurrence of any of the component events minus the date of randomization plus 1. If a patient has no component event by day 91, the time to event will be censored at the earlier of 90 days after randomization or the day of last available follow-up.

The changes in EQ-5D-5L index value and in EQ-VAS from randomization to day 7, will be compared between treatment groups using an appropriate contrast at day 7 from a mixed model for repeated measures (MMRM) for each outcome that includes the effects of the baseline value (EQ-5D-5L index or EQ-VAS as applicable), study center, treatment, visit, baseline value×visit and treatment×visit. EQ-5D index will be derived for each patient from the French value set. Patients who are missing a response due to death will be assigned the index value equivalent to death (0) and worst possible VAS score (0). The method assumes that missing data are missing at random (MAR) and the hypothetical treatment effect that is estimated is what would have been observed if all patients had continued on the assigned treatments for the full treatment period. Shifts in responses to each dimension from baseline to each time point will also be described.

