9.4.4 Safety Analyses

Adverse events will be coded using the Medical Dictionary for Regulatory Activities (MedDRA). The incidence of adverse events with an onset after randomization through 30 days post-randomization will be tabulated by system organ class and preferred term. All adverse events, fatal adverse events, serious adverse events will be summarized by treatment group. Treatment-related adverse events are those that are considered by the investigator as potentially, probably, or definitely related to the study intervention.

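### The Visit 6 telephone call, the last contact, may be made on time 5 days before the 90-day outcome period it must cover has ended

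*Protocol*

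**What the plan says.** **Outcomes to day 91.** Section 1.3 places Visit 6, a telephone contact, at "90 (+/- 5) days after randomization". No contact follows it, and under section 4.4 a participant who has had the last scheduled visit has completed the study. The only row of the Schedule with a separate mark at Visit 6 is clinical outcomes.

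The periods to be covered are fixed elsewhere:

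- Section 8.1.6: "Deaths will be recorded through 90 days post-randomization", with lengths of stay for "each rehospitalization through 90 days following randomization".
- Section 9.4.3: the first secondary endpoint counts a worsening heart failure (WHF) adverse event, heart failure readmission or "death from any cause from randomization through day 91 with a log-rank test stratified by study center". For a patient without an event, "the time to event will be censored at the earlier of 90 days after randomization or the day of last available follow-up".
- Section 9.4.9: items 2, 5, 6, 7 and 15 also run to day 91.

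**Adverse events to day 31.** Section 1.3 places Visit 5 at "30 (+/- 5) days after randomization". Section 8.3.4 has adverse events recorded up to day 31 or the last day of participation, and section 9.4.4 says: "The incidence of adverse events with an onset after randomization through 30 days post-randomization will be tabulated". Section 8.1.5 has WHF reported as an adverse event through day 31. Sections 8.2 and 8.3.4 have adverse events asked about at every study visit, the latter looking back to the previous visit.

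**The concern.** A symmetric window suits a measurement taken at a point in time, such as CRP or EQ-5D-5L, because being a few days early or late matters about equally. Visit 6 takes no such measurement. It looks back over a fixed period, and a look-back made before the period is over cannot be complete. A site can therefore follow the Schedule exactly and still leave the last days of the outcome period unobserved.

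What is at stake is modest: a little information in the secondary composite, and completeness of the day-91 death and readmission endpoints. It bears on the sponsor's own reasoning, because Amendment 1 moved the secondary endpoint to day 91 on the ground that few events were expected and a longer period should add power.

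The same mechanism arises at Visit 5 for adverse events, with the difference that a later contact exists. There the question is whether the protocol says clearly that this contact collects them. It also touches efficacy, since WHF adverse events enter the secondary composite.

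**Working it through.** **Inputs**

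- Day count (Summary of Changes): the assessments 30 and 90 days after randomization are those "which are days 31 and 91 counting the day of randomization as day 1". Study day 91 is thus 90 days after randomization, and study day 31 is 30 days after.
- Visit windows: section 1.3. Ends of the periods: sections 8.1.6, 9.4.3, 8.3.4 and 9.4.4.
- Patients: 120 (60 per group).
- Event rates: the protocol gives none for these endpoints, so ranges are assumed below.

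**The plan's own figure.** The only one is the power for day 7 CRP in section 9.2. Difference in logs: −ln(0.6) = 0.511. Standard error: 1.002 × √(2/60) = 0.183. Ratio: 0.511/0.183 = 2.79. Power: Φ(2.79 − 1.96) = 79.7%, or 79.1% by the noncentral t with 118 degrees of freedom. This agrees with the stated 80% or so, and nothing below changes it.

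**Step 1: the outcome gap.** Earliest on-time Visit 6: 90 − 5 = 85 days after randomization (study day 86). End of period: 90 days. Gap: 90 − 85 = 5 days, and 5/90 = 5.6% of the period.

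**Step 2: average loss.** Assume calls are spread evenly over ±5 days. Half are early, by 2.5 days on average, so the mean loss is 0.5 × 2.5 = 1.25 days per patient. That is 1.25/90 = 1.4% of follow-up, or 1.25 × 120 = 150 patient-days of 10,800 (120 × 90).

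**Step 3: first events in the gap, worst case.** Suppose all 120 patients are called at 85 days. With 90-day composite rate r and constant hazard, h = −ln(1 − r)/90, and the probability of a first event in the last 5 days is exp(−85h) − exp(−90h).

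| Assumed r | Probability | Patients of 120 | Share of all first events |
|---|---|---|---|
| 10% | 0.0053 | 0.6 | 5.3% |
| 20% | 0.0100 | 1.2 | 5.0% |
| 30% | 0.0140 | 1.7 | 4.7% |
| 40% | 0.0173 | 2.1 | 4.3% |

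**Step 4: adverse events.** Earliest on-time Visit 5: 30 − 5 = 25 days. End of period: 30 days. Distance: 5 days, or 5/30 = 16.7%. Whether this is a gap depends on Visit 6:

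- Sections 8.2 and 8.3.4 require the inquiry at each study visit, and the Schedule labels the call Visit 6. On that reading the days after Visit 5 are covered.
- In the Schedule, the clinical outcomes row has a separate mark at Visit 6 and the adverse events row shows none. On that reading a site would not ask.

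Only on the second reading, with every patient seen at 25 days and nothing reported in between, would first adverse events be missed. By the same formula over 30 days, assumed rates of 20%, 40% and 60% give about 3.6, 6.4 and 7.9 patients of 120. Deaths and readmissions in these days are not at issue, because Visit 6 collects clinical outcomes.

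**The case against.** **Censoring already deals with an early call.** For the log-rank test this stands. Section 9.4.3 counts only observed time, so an early call costs a little information and does not in itself bias the comparison. Censoring does not recover the unobserved days, however, and it does not complete the day-91 death and readmission endpoints.

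**Section 8.1.6 already obliges sites to record events through 90 days and to make every effort to obtain vital status.** This stands in part. The effort clause concerns vital status only and fixes no date, so it does not secure readmissions. No scheduled contact remains through which a site that calls at 85 days could meet the wider duty.

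**The effect is negligible.** It is small. The counts in Step 3 are a worst case, and constant hazard probably overstates them: section 2.1 cites 10–14% worsening by day 7 and 30% rehospitalization within a month, which points to risk concentrated early. The case for change rests on how little it costs.

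**For adverse events a later contact exists.** This stands. A reader might infer from the Visit 5 window that nothing can pick up adverse events between an early visit and day 31. Sections 8.2 and 8.3.4 do not support that, since they can be read to require the inquiry at Visit 6. The adverse events row of the Schedule is also drawn as an arrow, so the absence of a mark is weaker evidence than a blank cell. What remains is an inconsistency to reconcile.

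**Conclusion.** The point holds for Visit 6. Its window lets a compliant call take place up to 5 days (5.6%) before the 90-day outcome period ends, and no contact follows. The 5-day maximum is plain date arithmetic. The 1.25-day mean assumes calls spread evenly over the window. The 0.6 to 2.1 first events assume every call at the earliest date, constant hazard and 90-day rates of 10% to 40%. The secondary composite loses a little information, the day-91 death and readmission endpoints are left incomplete, and the primary CRP analysis is untouched. This is a minor improvement.

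For adverse events the finding is narrower: section 1.3 and sections 8.2 and 8.3.4 need to be reconciled on whether Visit 6 asks about onsets up to day 31.

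Two stronger inferences are not supported:

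- That the 30-day adverse event percentages are understated. This would follow only if Visit 6 asked nothing and the events surfaced in no other way; section 9.4.4 also states no denominator.
- That the loss differs between arms because the trial is open-label. The windows are the same in both arms, and nothing in the protocol indicates that one arm would be called earlier.

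**What to change.** 1. **Visit 6.** In section 1.3, let the window open at 90 days, for example 90 (0 to +10) days, which keeps the present 10-day width; 0 to +5 would also close the gap. Every on-time call then covers the whole period. Section 9.4.3 already stops counting at 90 days, so later calls do not lengthen the endpoint. With 0 to +10, the latest call moves from 95 to 100 days after randomization, and recall is slightly longer.

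2. **Adverse events.** Keep the Visit 5 window, which suits its measurements. State in sections 1.3 and 8.3.4 that the Visit 6 call asks about adverse events, including WHF, with onset after Visit 5 and up to day 31. This adds one question to an existing call. The drawback is longer recall for those few days.

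Neither change adds visits or patients, and the power for the primary endpoint stays as it is.
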